9. 9. 9.	CONFIDENTIALITY REGISTRATION WITH CLINICALTRIALS.GOV SOURCE DOCUMENTS 9.3.1. Research Electronic Data Capture (REDCap) and origination of electronic source data 9.3.2. Paper source data 9.3.3. Handwritten entries 9.3.4. Remote and/or virtual research interactions DATA MANAGEMENT RECORDS RETENTION	22 22 23 23 23
10.	STUDY MONITORING, AUDITING, AND INSPECTING	
	STUDY MONITORING PLAN AUDITING AND INSPECTING	
11.	ETHICAL CONSIDERATIONS	24
12.	STUDY FINANCES	25
	FUNDING SOURCE CONFLICT OF INTEREST SUBJECT STIPENDS OR PAYMENTS	25
13.	PUBLICATION PLAN	25
14.	REFERENCES	26
15.	ATTACHMENTS	28
SUN	MARY OF PROTOCOL CHANGES	29

HSC 20190766H Page vi

Version: 2.4_10-29-2020

List of Abbreviations

SGLT: Sodium-glucose co-transporter T2DM: Type 2 Diabetes Mellitus

AGE: Advanced Glycation End products
RAGE: Receptor for Advanced Glycation End products

GFR: Glomerular Filtration Rate OGTT: Oral Glucose Tolerance Test CPET: Cardio Pulmonary Exercise Test

Study Summary

Title	Effect of SGLT2 inhibition on aging-related biomarkers in older obese adults with pre-diabetes
Protocol Number	HSC20190766H
Phase	2b Pilot
Rationale	Inhibitors of the sodium-glucose co-transporter (SGLT2) are FDA-approved for the treatment of type 2 diabetes (T2DM). Their mechanism of action involves lowering of blood glucose concentration secondary to increased glucose excretion of glucose by the kidney. These drugs also improve body weight, blood pressure, and cardiac function. Based on these pleiotropic effects, including its calorie restriction-mimetic properties, we hypothesize that SGLT2 drugs will impact several basic aging-related processes, including reductions in oxidative damage to DNA and proteins, advanced glycation end products (AGE) and receptor for AGE (RAGE), cellular senescence, and mitochondrial function.
Study Duration	Treatment duration 12 weeks; complete study participation up to 6 months
Study Center(s)	UTHSCSA (MARC, FORU, BICRC)
Objective	Primary Endpoint: Determine if dapagliflozin significantly reduces aging-associated biomarkers (AGE-RAGE, oxidative stress in DNA and protein, cellular senescence, skeletal muscle mitochondrial function.) Secondary Endpoint: Determine healthspan benefits of dapagliflozin treatment (VO ₂ Max, insulin sensitivity, 6-minute walk test, grip strength, quadriceps strength)
Number of Subjects	20
Inclusion Criteria	Men and post-menopausal women age 60 and above; BMI 30-38 (BMI 29.5 will be rounded up); diagnosis of pre-diabetes (HbA1c 5.7-6.4%); stable body weight (±3% for ≥3 months); Montreal Cognitive Assessment 21 and above; Subjects must be in good general health as determined by physical exam, medical history, blood chemistries, CBC, TSH, lipid profile, EKG and urinalysis.
Exclusion Criteria	Diagnosis of diabetes based on ADA criteria; impaired renal function with eGFR < 45 mL/min/1.73m²; impaired liver function with labs 3x ULN and above; hematocrit with LLN 30% and below; triglycerides with ULN 600 mg/dL and above; abnormal TSH of 0.3 and below to 10 and above; urinalysis with >5-10 WBC; history of frequent UTI; poorly controlled blood pressure (sysBP >180, diaBP > 100 mmHg); history of recent cardiovascular event in prior 6 months, heart failure, active heart disease; current treatment with drugs known to affect glucose and lipid homeostasis; current treatment with anticoagulants (aspirin <326 mg and clopidogrel permitted if held 7 days prior to biopsies; active inflammatory, autoimmune, gastrointestinal, hepatic, infectious, malignant or uncontrolled psychiatric disease (controlled depression, anxiety, PTSD, etc. enrollment allowed); ; blood donation within 2 months prior to enrollment.
Concomitant Medications	Allowed: Standard of care medications for the management of hypertension, hyperlipidemia and other drugs that at the discretion of the investigator will not interfere with the results of the study. If patient on drugs that affect metabolism like levothyroxine, should be on a stable dose for the last 3 months. Prohibited: Any medications known to adversely affect glucose and lipid metabolism. Additionally, patients on warfarin or other blood thinners except for aspirin up to 325mg and clopidogrel will be excluded.

Study Product, Dose, Route, Regimen	Dapagliflozin, 10mg, Oral, Daily
Duration of administration	12 weeks
Statistical Methodology	Comparisons of means between all the groups will be done by ANCOVA. Associations, within a group, between aging-related biomarkers vs metabolic outcomes and vs. healthspan outcomes will be determined by Pearson's correlation. For tests of correlation coefficients between groups, we will use the Fisher's Z transformation. We will also determine the relationship between aging-related biomarkers vs metabolic outcomes and vs. healthspan outcomes, by using multiple regression analysis. Scatter plots will be done to look for outliers and to verify linearity.

HSC 20190766H Version: 2.4_10-29-2020

1. Introduction

This document is a protocol for a human research study. This study will be conducted according to Good Clinical Practice guidelines as adopted by FDA, applicable government regulations, and Institutional research policies and procedures.

1.1. Background

Type 2 diabetes mellitus (T2DM) occurs in 9% of the US population, affects ~30 million individuals and its prevalence has increased dramatically (1) due to multiple factors: (i) increased longevity, (ii) increased incidence of obesity, (iii) decreased physical activity, (iv) rapid growth of minority populations at high diabetes risk. T2DM patients experience significant morbidity and mortality from microvascular and macrovascular complications. The cost of treating diabetes and associated complications in 2007 was \$174 billion and is predicted to double by year 2030 (2).

The Diabetes Control and Complications Trial (DCCT) (3) and United Kingdom Prospective Diabetes Study (UKPDS) (4,5) have documented that hyperglycemia is the major risk factor for microvascular and, to lesser extent, macrovascular (6,7) complications. Insulin resistance and impaired insulin secretion are characteristic features of T2DM (8,9,10). The earliest expression of this insulin resistance and impaired insulin secretion is called prediabetes. Prediabetes is characterized either by impaired fasting glucose (IFG) or abnormal plasma glucose after a 75gm oral glucose tolerance test (OGTT) or an A1c value of 5.7% to 6.4% There are approximately 84.1 million adults with prediabetes (33.9% of the population) and 23.1 of these adults are 65 years or older (1). Prediabetes has been shown to increase the risk of developing type 2 diabetes, heart disease and stroke. Other classic cardiovascular risk factors are frequently present in prediabetic individuals including classic hypertension, dyslipidemia, procoagulant state, obesity, endothelial dysfunction, insulin resistance, and inflammation (3,4). Since most of the morbidity and mortality in T2DM arises from long term complications, early detection and effective intervention to delay or prevent development of T2DM would be expected to have enormous beneficial clinical, social and economic impact.

The inhibitors of the sodium-glucose co-transporter-2 (SGLT2i) are FDA-approved for the treatment of type 2 diabetes (T2DM). This class of drugs have a unique mechanism of action that involves lowering of plasma glucose concentration secondary to an increase in glucose excretion by the kidney. This glucosuric effect results in a durable reduction in HbA1c, weight loss, improved insulin sensitivity, and enhanced beta cell function (11). Beyond the glucocentric effects of SGLT2i, they have now been shown in patients with cardiovascular disease (CVD) to reduce mortality and hospitalization for heart failure and provide renal protection. A variety of potential mechanisms have been invoked to explain the beneficial effects of SGLT2i on CV mortality and hospitalization for heart failure and these have been the subject of recent reviews (12,13,14). Of the potential mechanisms responsible for the improved CV benefit, hemodynamic factors, including the simultaneous reduction in preload (12) (secondary to mild intravascular volume depletion) and afterload (secondary to reduced blood pressure (12) and improved aortic distensibility (15) most commonly have been cited. These attributes have elevated SGLT2i's to second- or third-line therapy for the treatment of T2DM patients in patients with or without CVD (16,17,18).

1.2. Innovation

Investigations into the aging process have identified major cellular dysfunctions that contribute to aging, including but not limited to increased burden of damaged DNA and protein, reduction in mitochondrial respiration, and the development of pro-inflammatory senescent cells (19). Developing and testing interventions that interact with multiple points of this spectrum may delay the aging process. Based on prior investigations, we believe the SGLT2 inhibitor class of drugs may target these basic mechanisms involved in the aging process and propose testing in a high-risk human population to evaluate their effectiveness in

Page 4

Version: 2.4 10-29-2020

ameliorating aging-associated dysfunctions. Specifically, we hypothesize that SGLT2i drugs will lead to reductions in oxidative damage to DNA and proteins, AGE-RAGE, and cellular senescence, which will be accompanied by improvements in mitochondrial function. If our hypothesis is correct, these findings could lead to the development of new approaches to increase both healthspan and lifespan.

1.3. Preliminary data

SGLT2 inhibitors have shown effects on systemic and tissue low-grade inflammation (20) In the CANTATA-SU study, 52 weeks of canagliflozin 300 mg daily to individuals with T2DM decreased IL-6 by 22% and CRP by 4.4% versus glimepiride (21) (Figure 1). CRP and other inflammatory marker data following SGLT2 administration are relatively scarce in humans, but in animals, several reports have shown reductions in cytokine and chemokine concentrations in parallel with protective effects against progression of atherosclerotic lesions (20). Experimental findings in rodents also suggest that part of the renoprotective effects of SGLT2 inhibition may be related to anti-inflammatory and anti-fibrotic actions at the kidney level. Entry of glucose into the tubule cells

may induce inflammatory and fibrosis genes, as well as increase apoptosis. Experimental administration of an SGLT2i prevents tubulointerstitial injury in obese T2DM mice (22). Underlying mechanisms to explain this antiinflammatory effect are varied, but may involve weight loss, reduction in adipose tissue inflammation and attenuation of oxidative stress (20).

It is clear that the elevated glycemia can accelerate the formation of advanced glycation end-products (AGE's) (23). There is also evidence that engagement inflammatory biomarkers at Week of the AGEs receptor (RAGE) by AGE's may elicit oxidative stress as well as generation of inflammatory and fibrotic reactions in tissues (23), Importantly, these implicated AGEs inflammatory/fibrotic pathways cause widespread tissue damage including the pancreatic beta-cells, renal

the risk of complications of diabetes such as nephropathy, neuropathy, and retinopathy, and the development of CVD (24). In addition, RAGE may play a critical role in reactive oxygen species (ROS) production. RAGE expression and activation may worsen AGE accumulation through decreased expression of key antiglycation enzymes (23).

The effects of SGLT2i on AGEs have yet to be extensively studied in humans, though we have shown that these drugs additionally increase mitochondrial fatty acid oxidation, cause a small increase in ketone levels, a decrease in uric acid levels and are associated with attenuation of oxidative stress (25). Terami et al., showed in male db/db mice given SGLT2i for 12 weeks that SGLT2i reduced renal mesangial matrix expansion and renal fibrosis. Proinflammatory genes, oxidative stress, and apoptosis were all decreased in renal tissue. In addition, SGLT2i restored pancreatic beta-cell mass to non-diabetic (non-diabetic db/m mice) levels (26). In streptozotocin-induced diabetic rats (STZ) treated for 4 weeks of SGLT2i versus a placebo buffer, SGLT2i decreased the expression levels of AGEs, and its receptor (RAGE) and other markers of oxidative stress at the kidney level (27) (Figure 2). Additionally, Osorio et al. reported in a similar streptozotocin-induced diabetic rat model that SGLT2i restored several oxidative stress markers to control levels and prevented renal tissue 3-nitrotyrosine rats+empagliflozin accumulation, a tissue marker of oxidative stress (28).

In prediabetes there is limited information regarding the role of SGLT2 inhibitors.

but the available data in humans show that prediabetic obese subjects treated with an SGLT2i had significant reductions in weight (29), which is an independent CV risk factor (30) and is associated with insulin resistance,

[figure not shown]
[figure not shown]

Figure 1. Effects on Inflammatory Biomarkers at Week Canagliflozin 300 mg was associated with a 22% reduction in median serum IL-6 compared to glimepiride. Change from baseline in serum 52. IL-6, interleukin-6.

cells, and the vascular system. This directly or indirectly increases the risk of progression to T2DM, increases

2. **Effects Figure** of empagliflozin on AGE-modified protein levels and immunostaining. Total RNAs extracted from the kidney of STZ STZ and with RNAqueous-4PCR kit.

Version: 2.4 10-29-2020

diabetes, dyslipidemia, hypertension, cancer, stroke and nonalcoholic fatty liver disease (31-34). It is likely that the other known glucose and non-glucose lowering effects of SGLT2i could be extrapolated to prediabetic individuals.

1.4. Dose Rationale and Risk/Benefits

In the DPP trial, weight loss was proportional to diabetes prevention. There are no serious risks to losing weight at a reasonable rate. Dapagliflozin 10mg daily is the maximum daily dose and has been shown to increase glucose urinary excretion more than 5mg daily. Dapagliflozin 10mg/day has been assessed in combination with exenatide treatment in prediabetic patients for one year and shows similar safety and tolerability to previous trials in diabetic patients (35). Dapagliflozin 10mg/day is also in use for the DAPA-HF study in a study population that includes prediabetics (36). Another SGLT2i, empagliflozin, has been assessed in prediabetics at a comparably high dose (25mg/day) for two weeks and did not show AE among treated subjects (37). The SAE's associated with dapagliflozin include acute kidney injury, fall from orthostasis, gangrene of the perineum, and diabetic ketoacidosis. These risks will be mitigated in this study by monitoring subject status with biweekly phone check-ins with patients as well as monthly in-person visits during drug refill visits.

2. Study Objective

The primary objective is to determine whether SGLT2 inhibitors improve biomarkers of aging in older obese adults with pre-diabetes.

The secondary objective is to determine whether changes in aging-related biomarkers resulting from SGLT2i therapy are linked to changes in glucose metabolism and healthspan.

3. Study Design

3.1. Subjects

Recruited subjects for this study will be men and post-menopausal women aged 60 years and above, with a diagnosis of obesity as measured by BMI (30-38 kg/m²; BMI ≥29.5 will be rounded up) and who qualify as prediabetic (HbA1c 5.7-6.4%). Screening at visits 1 and 2 will identify participants who meet entry criteria for the study. The target enrollment for this pilot study is 20 completed subjects, split evenly between experimental and control groups. Because this study seeks to identify novel SGLT2i effects on biomarkers of aging, we do not have direct data on the potential impact of dapagliflozin on biomarkers such as cellular senescence, AGE-RAGE, or mitochondrial function to power our study.

3.2. General Design

This is a single center, open-label, randomized controlled trial. 20 completed subjects are planned. Each subject will be randomized to either the experimental group of dapagliflozin 10mg daily for 12 weeks or the control group of nutritional counseling for weight loss. Healthspan and clinical evaluations will be taken at baseline and at weeks 10-12 of the study.

Screening data will be reviewed to determine subject eligibility. Subjects who meet all inclusion criteria and none of the exclusion criteria will be entered into the study.

The following treatment regimens will be used:

- Dapagliflozin: 10mg per day for 12 weeks. Subjects will return to refill drug medication and perform compliance check at 4 weeks and 8 weeks after beginning treatment.
- Control Group: Subjects will meet with a dietitian every 1-2 weeks throughout the study to discuss nutritional counseling with a goal to lose 3-5% of body weight over 12 weeks to mirror expected SGLT2

inhibitor-derived weight loss over the same period. During these hour-long sessions, volunteers will learn how to adjust their eating habits by following the recommendations of the American Heart Association for reducing dietary fat and substituting complex carbohydrates and reducing energy intake to induce gradual weight loss while maintaining recommended dietary composition. Volunteers also will receive education on portion sizes, meal timing, and meal preparation. Participants receive a notebook of course content and will weigh in prior to each session. Additional counseling visits and/or phone calls may be instituted if desirable weight loss is not achieved. Subjects may be asked to record their dietary intake for a 24-hour period throughout the intervention for review by the dietitian.

Total duration of subject treatment will be 12 weeks. Total duration of the study is expected to be 16-18 weeks.

3.3. Study Endpoints

Primary outcome: The primary endpoint for this study is a reduction in urine AGE-RAGE measurements as a result of dapagliflozin treatment. We will be assessing AGE-RAGE in all subjects at baseline and after intervention

Secondary outcomes: Mitochondrial function: This measurement will assess changes in muscle mitochondrial respiration after dapagliflozin treatment. Measurements will occur using muscle samples obtained at baseline and after intervention.

Insulin Sensitivity: This measurement will be obtained before and after the intervention using the HOMA-IR index derived from the fasting insulin and glucose concentrations.

Oxidative Stress: This measurement will be assessed in muscle samples obtained at baseline and after intervention.

Healthspan Measurements: These assessments will include grip strength, isometric knee extension, 6-minute walking distance, and a VO₂Max obtained from CPET. We will be assessing these outcomes in all subjects at baseline and after intervention. Measurements obtained from these exams will evaluate the effect of dapagliflozin treatment on physical indicators of aging.

Cellular Senescence: Senescent cell burden will be assessed in adipose tissue obtained at baseline and after intervention, using both senescence-associated beta-galactosidase staining as well as senescence-associated gene expression assays.

DNA methylation: DNA methylation, a key biological marker of aging, will be evaluated in peripheral blood cells before and after intervention.

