Fat (fresh): tissue will be subjected to beta galactosidase staining to test cellular senescence in the tissue as described previously (42).

Blood/plasma: Circulating factors that include inflammatory markers IL-6 and IL-6R, AGE-RAGE levels, and SASP biomarkers such as plasminogen activator inhibitor (PAI) -1 and 2, intracellular adhesion molecule (ICAM)-1 and 2 will be tested using ELISA kits on blood samples obtained during study. 20mL of blood will be drawn (two (2) 10mL EDTA lavender top tubes), centrifuged to obtain 10mL of plasma, and stored in 0.5-1 ml aliquots to evaluate whether the treatment reduces pro-inflammatory blood markers of aging. Blood samples obtained during the glucose tolerance tests will be analyzed for insulin and free fatty acid concentrations. DNA methylation assays will be done in peripheral blood cells.

Urine: A fasted urine sample will be obtained at baseline and post treatment for urinalysis, microalbumin, excreted IL-6, and AGE-RAGE levels to evaluate changes with treatment. 2-5 ml aliquots will be stored frozen for analysis.

^{**}Visits 2 and 3 may be performed interchangeably

^{***}Visits 8 and 9 may be performed interchangeably

7. Statistical Plan

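### The Study Summary and section 3.3 name different primary endpoints, and the urine AGE-RAGE measure is under-specified, with no stated correction for urine concentration

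*Combined protocol and SAP*

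**What the plan says.** **Primary endpoint.** Section 3.3 (Study Endpoints) names one variable: "The primary endpoint for this study is a reduction in urine AGE-RAGE measurements as a result of dapagliflozin treatment". It lists mitochondrial function, oxidative stress and cellular senescence as secondary outcomes. The Objective row of the Study Summary reads: "Primary Endpoint: Determine if dapagliflozin significantly reduces aging-associated biomarkers (AGE-RAGE, oxidative stress in DNA and protein, cellular senescence, skeletal muscle mitochondrial function". Section 2 gives the primary objective only as ageing biomarkers in general, and section 7.2 names no primary variable.

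**Measurement.** The urine paragraph of section 6.3 (Analyses) says: "A fasted urine sample will be obtained at baseline and post treatment for urinalysis, microalbumin, excreted IL-6, and AGE-RAGE levels". It adds that "2-5 ml aliquots will be stored frozen for analysis". The blood paragraph of the same section also lists AGE-RAGE: "Circulating factors that include inflammatory markers IL-6 and IL-6R, AGE-RAGE levels". The Study Summary does not say whether it means urine or plasma.

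**Drug action.** Section 1.1 describes glucose lowering "secondary to an increase in glucose excretion by the kidney" and, among proposed cardiovascular mechanisms, reduced preload "secondary to mild intravascular volume depletion". Section 1.4 says the 10 mg dose "has been shown to increase glucose urinary excretion more than 5mg daily". Under section 3.2 the control arm receives nutritional counselling and no study drug.

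**Analysis.** Section 7.2 plans ANCOVA, without listing covariates, and natural logs for median percent change. It calls the study exploratory and not powered for p <0.05. Section 7.1 says the data will inform the sample size of later studies.

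**The concern.** Two questions about the primary result are open.

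First, which result may be called primary? With one text naming a single urine measure and the other naming four families, any of the four could be presented as primary after the data are seen, and each choice could be defended from the protocol.

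Second, does a between-arm difference in urine AGE-RAGE reflect AGE-RAGE at all? The level in a single urine sample depends on the amount excreted and on how concentrated the urine is. If treatment changes urine concentration in one arm only, the measured level moves even when excretion does not. That change arises after randomisation, so neither randomisation nor adjustment for baseline removes it. A log transformation turns a multiplicative shift into an additive one and leaves it in the estimate. An estimate distorted in this way would carry into the planning of the later trial.

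**Working it through.** **1. Status of each family, side by side.** Both texts are current in version 2.4, and the summary of changes does not explain the difference.

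| Family | Study Summary | Section 3.3 |
|---|---|---|
| AGE-RAGE | primary, urine or plasma not stated | primary, urine |
| Oxidative stress | primary | secondary |
| Cellular senescence | primary | secondary |
| Mitochondrial function | primary | secondary |

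**2. What AGE-RAGE denotes.** The abbreviation list and the Rationale expand AGE and RAGE separately, as products and receptor. This leans towards two results. No section says so, and none gives an assay or unit for the urine measure. The sample-use lists for Visits 5 and 11 (sections 6.1.5 and 6.1.11) do not mention AGE-RAGE, although urine is collected at both.

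**3. Correction for concentration.** Sections 3.3, 6.2, 6.3 and 7.2 mention no urine creatinine, specific gravity, osmolality, volume or timed collection used to adjust AGE-RAGE. The metabolic panel in section 6.2 is a blood test and does not serve. Microalbumin might be reported per creatinine, but the documents do not say.

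**4. Size, by illustration.** The plan has no figure to reproduce, and the flow changes and SDs below are assumptions. With excretion E unchanged and flow V multiplied by (1+v), concentration E/V changes by 1/(1+v) − 1.

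| Assumed flow change v | Change in concentration |
|---|---|
| +10% | −9.1% |
| +20% | −16.7% |
| +30% | −23.1% |
| −10% | +11.1% |
| −20% | +25.0% |
| −30% | +42.9% |

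To set this against the noise, take 10 completers per arm (section 3.1: 20, split evenly) and a two-sample comparison of log changes, with SE = SD × √(2/10), 18 df and t = 2.101. The 95% CI around a ratio of 1.00 is exp(±2.101 × SE). The shift in SE units is |ln(1+v)|/SE, where ln 1.2 = 0.182 and |ln 0.8| = 0.223.

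| Assumed SD of log change | SE | 95% CI around 1.00 | Shift, v = +20% | Shift, v = −20% |
|---|---|---|---|---|
| 0.25 | 0.1118 | 0.79-1.26 | 1.63 SE | 2.00 SE |
| 0.4 | 0.1789 | 0.69-1.46 | 1.02 SE | 1.25 SE |
| 0.7 | 0.3130 | 0.52-1.93 | 0.58 SE | 0.71 SE |

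ANCOVA with one baseline covariate would have 17 df and a residual SD, which changes these figures little.

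**5. What creatinine does.** If analyte and creatinine share a sample, flow cancels: (E_A/V)/(E_Cr/V) = E_A/E_Cr. A within-sample ratio of two urine analytes is already free of flow. Dividing that ratio by creatinine would multiply it by (1+v) and so introduce the error.

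**6. Limit of the correction.** If creatinine output falls by 5% or 10% in one arm, the corrected value rises by 1/0.95 − 1 = 5.3% or 1/0.90 − 1 = 11.1%.

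**The case against.** The study is a 20-person pilot, declared exploratory, with no decision rule. The Study Summary text sits in a row headed Objective and resembles the broad aim in section 2, while section 3.3 is the dedicated endpoint section and is clear on its own. All of this is fair, and it makes the endpoint conflict a matter of definition and reporting. The conflict still needs resolving, because the Study Summary text is labelled as an endpoint and contradicts section 3.3.

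Three stronger readings are tempting.

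- A reader might infer an inflated false-positive rate from four primary families, particularly as the Study Summary speaks of significant reductions. The documents do not support this. They set no alpha and no significance-based decision, and section 6.3 lists several assays in some families, so a calculation with one test per family does not describe the plan.
- A reader might infer that dapagliflozin dilutes the urine and so produces a spurious fall, in the direction of the endpoint. Sections 1.1 and 1.4 speak of glucose excretion and mild volume depletion. They give no change in urine flow or concentration for a fasted sample in this population, so direction and size are unknown.
- A reader might call the endpoint wholly undefined. The separate expansions of AGE and RAGE narrow it. What is missing is the number of results, the assay and the unit.

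It is also fair that creatinine is not a neutral denominator: both arms are expected to lose weight, and the correction could raise the SD. A timed excretion rate would avoid this, but no timed collection is described and stored aliquots cannot supply one. The objection supports showing both scales. It does not support leaving the handling of urine concentration unstated.

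**Conclusion.** The conflict between the Study Summary and section 3.3 is certain from the text and must be reconciled. The omission of any urine-concentration correction is equally certain, as is the missing statement of what urine AGE-RAGE comprises.

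Whether the omission biases the result is conditional. It requires that the measure be one or more concentrations and that treatment change urine concentration. Under those conditions neither ANCOVA nor logs protects the comparison. Every figure above is an illustration. Across the assumed SDs, a 20% flow change ranges from a shift well inside the noise (0.58 SE) to one of about two standard errors. If the measure is a within-sample ratio, dilution cancels and the urine point reduces to saying so.

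The point is worth fixing because the data are meant to guide later studies and the change is cheap. It does not invalidate the trial.

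**What to change.** 1. **Make the Study Summary and section 3.3 name the same primary.** Following section 3.3, as the dedicated endpoint section, this is urine AGE-RAGE, stated as urine, with the other three families secondary. State whether AGE and RAGE are one result, two results or a ratio, with assay and unit. If they are two results, name one as primary.

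2. **State how urine concentration is handled.** For each urine concentration, including urine IL-6, measure creatinine in the same stored aliquot. Analyse the log analyte-to-creatinine ratio by ANCOVA with log baseline as covariate, and report a between-arm ratio with 95% CI. Beside it, show the uncorrected level and urine creatinine by arm and visit, which shows directly whether urine concentration differed. Show plasma AGE-RAGE as supportive. If AGE-RAGE is a within-sample ratio, do not divide it by creatinine.

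**Cost.** Wording, plus at most one inexpensive assay on aliquots the plan already stores, and possibly none if the laboratory already reports microalbumin per creatinine. No new visit or sample is needed. The downside is that creatinine output may shift with weight, muscle or kidney function, which is why both scales should be shown.
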